7.4.1 Removal of Mirena

Timing of removal

- Mirena should not remain in the uterus after 8 years.
- If pregnancy is not desired, the removal should be carried out during menstruation, provided the woman is still experiencing regular menses. If removal will occur at other times during the cycle, start a new contraceptive method a week prior to removal. If removal occurs at other times during the cycle and the woman has had intercourse in the week prior to removal, she is at risk of pregnancy. See also section [8.2](#).

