- a An End-of-Treatment Visit must be performed also for all subjects who discontinue treatment. If a subject prematurely discontinues treatment, all efforts should be made to perform all the assessments scheduled for this EOT visit (Visit 8) including the EOS phone contact 3 weeks after the removal of Mirena before the subject is withdrawn from the study.
- b For subjects who prematurely discontinued study treatment unless the reason for discontinuation is “pregnancy”, “death”, or “withdrawal by subject” where the subject has withdrawn main consent during study conduct and wishes to stop future contact with the site. Subjects that had withdrawn consent during study, but consented to post study participation follow-up will be contacted at this point. See also Section 9.4.1.
- c Subjects that prematurely discontinued treatment due to ‘Wish for pregnancy’ will be contacted. If a subject was not pregnant at 3 month contact and no longer wished to become pregnant, a 12-month contact is not required. If a subject was “Lost to Follow-up” at 3 month contact, a 12-month contact is required. See also Section 9.4.1.
- d The baseline visit (Visit 2) should take place 14 to 0 days before the end of Year 5 of Mirena use.
- e A cervical smear should be taken at the Screening Visit or a documented normal result must have been obtained not more than 6 months before screening. Subjects with ASCUS can be included if they have an HPV DNA test that, according to the standards of the central or local laboratory, is negative for high-risk HPV strains. A single repeat test is permissible if the screening results are abnormal.
- f If Chlamydia test is positive, also test for gonorrhea. A single repeat test is permissible if the screening results are positive
- g In addition to the urine pregnancy tests performed by the site at each study visit, subjects will be given home urine pregnancy tests to be used whenever a pregnancy is suspected. Subjects must contact the study site immediately if a pregnancy test is positive. Home pregnancy test is to be done on the day of the 3-week contact.
- h PK sampling: All subjects: one sample to be taken at baseline and at EOT (or if subject prematurely discontinues prior to removal) per subject; and two randomized samples to be taken at two of the visits 3 – 6.
- i PK sampling for subjects randomized to this visit.

d=day, EOS=end of study, EOT=end of treatment, mo=month, PK=pharmacokinetics, wks=weeks, y=year

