9.2 Visit description

General information

Timing of the visits

If not stated otherwise, the measures listed in the following sections will be performed by or under the supervision of a study site investigator.

There will be 8 scheduled study visits: screening visit (Visit 1), baseline visit (Visit 2), 5 visits during the treatment phase (Visit 3 to 7) and the end-of-treatment visit (EOT, Visit 8). The end-of-study visit (EOS) is a phone contact at 3 weeks after the EOT (all subjects).

In addition, there will be up to 2 follow-up contacts for post-treatment pregnancy tracking. 3-month follow-up contact is for subjects who prematurely discontinued study treatment unless the reason for discontinuation is “pregnancy”, “death”, or “withdrawal by subject” where the subject has withdrawn main consent during study conduct and wishes to stop future contact with the site. For subjects that had withdrawn consent during study, but consented to post study participation follow-up, will be contacted. If subjects could not be contacted at 3 months, they will be considered “Lost to Follow-up” for post-study pregnancy tracking. 12-month contact is for subjects that prematurely discontinued treatment due to ‘Wish for pregnancy’. If a subject was not pregnant at 3-month contact but subject no longer wished to become pregnant, a 12-month contact is not required. If subject was “Lost to Follow-up” at 3 months, a 12-month contact is required. For details, see Section 9.4.1.2.

The screening period can start when the subject has had the Mirena in place for 4 years and 6 months. Screening period is up to 6 months. Screening activities should be completed within 60 days after signing the informed consent. The baseline visit (Visit 2) should take place 14 to 0 days before the end of Year 5 of Mirena use.

The timing of the visits is based on the date of the baseline visit. Treatment period starts at the baseline visit (Visit 2, defined as Study Day 1).

The following visit windows are allowed:

- Visits 3 to 7 (during treatment) should be performed ± 2 weeks of the scheduled day.
- Visit 8 (EOT) should be performed at the earliest 2 weeks before the scheduled day and not later.
- Follow-up contact (EOS) should take place 3 weeks after the EOT (-3 day window allowed).

Unscheduled visits

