Subjects who prematurely discontinued study treatment will be contacted by phone unless the reason for discontinuation is “pregnancy”, “death”, or “withdrawal by subject” where the subject has withdrawn main consent during study conduct and wishes to stop future contact with the site. For subjects that had withdrawn consent during study, but consented to post study participation follow-up, post treatment pregnancy tracking information is expected. At this time, subjects will be asked if they have been pregnant after the study (i.e. after the 3-week follow-up call). This contact is part of the Post-Treatment Pregnancy Tracking (PTPT) process, see Section 9.4.1.

9.2.12 12-month follow-up contact for return-to-fertility

This section was changed in Amendment 1, see Section 15.1.1.6.

Subjects that prematurely discontinued treatment due to ‘Wish for pregnancy’ will be contacted and asked about pregnancies that occurred within 12 months after end of treatment (EOT, i.e. removal of Mirena). If a subject was not pregnant at 3 month contact and no longer wished to become pregnant, a 12-month contact is not required. If subject was “Lost to Follow-up” at 3 months, a 12-month contact is required. This contact is part of the Post-Treatment Pregnancy Tracking (PTPT) process, see Section 9.4.1.

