9.4.1.2 Pregnancies occurring after the end of study treatment

This section was changed in Amendment 1, see Sections 15.1.1.5 and 15.1.1.6.

All pregnancies detected up to 3 months after the removal of the Mirena must be reported to the sponsor; all subjects will be instructed to contact the investigator immediately if they

become pregnant less than 3 months after the removal of the Mirena. If the estimated date of conception is suspected to have occurred during study treatment (i.e. up to 7 days after EOT), further investigations will be conducted, and the pregnancy should be reported immediately and will be followed up according to the process described above for pregnancies during the study.

3-month follow-up contact: In addition, subjects who prematurely discontinued study treatment will be contacted unless the reason for discontinuation is “pregnancy”, “death”, or “withdrawal by subject” where the subject has withdrawn main consent during study conduct and wishes to stop future contact with the site. For subjects that had withdrawn consent during study, but consented to post study participation follow-up, post-treatment pregnancy tracking information is expected and they will be contacted by phone at 3 months after the removal of the Mirena. At this time, subjects will be asked if they have been pregnant after the study. If subjects could not be contacted at 3 months, they will be considered “Lost to Follow-up” for post-study pregnancy tracking.

12-month follow-up contact: Only subjects that prematurely discontinued treatment due to ‘Wish for pregnancy’ will be contacted and asked about pregnancies that occur within 1 year after end of treatment (EOT). If a subject was not pregnant at 3 month contact and no longer wishes to become pregnant, a 12-month contact is not required. If subject was “Lost to Follow-up” at 3 months, a 12-month contact is required.

PTPT information, i.e. data collected at the 3- and 12-month follow-up contacts, including information on all pregnancies identified, must be reported to the sponsor via electronic data collection tool (see Section 11.1). In addition, if the estimated date of conception is suspected to have occurred during study treatment, the pregnancy should be reported immediately according to the process described under section 9.4.1.1.

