A pregnancy will be allocated to the time period(s) that are relevant for the calculation of the PIs described above, e.g., a pregnancy that occurs on day 400 will be relevant for the 7th year PI, the two years PI (6th and 7th year), the three years PI (6th, 7th and 8th year), and the overall PI. Pregnancies that occur before Day 1 Year 6 of Mirena use will not count for the 1-year PI, 2-year PI and 3-year PI. Pregnancies that occur after the Mirena was removed or an expulsion was realized will not count for any PI.

It should be noted that e.g., pregnancies that occur after partial expulsion, but before Mirena removal will count for the PIs.

Furthermore, it should be noted that pregnancies that occur within 7 days after the end of exposure will count for the PIs.

Exposure times to be subtracted:

Subjects who apply additional concomitant contraception are not in risk or are under a lower risk of getting pregnant than subjects who do not apply additional contraception. In case a subject uses concomitant contraceptive methods (e.g., condoms to prevent STD); the respective 28-day reference period(s) of additional contraceptive method use will be excluded from the exposure time, unless a pregnancy occurred in that 28-day reference period.

Primary analysis

The primary method for the evaluation of the occurrence of pregnancy is the Pearl index defined as the number of pregnancies per 100 women years.

The PIs and the corresponding 2-sided 95 % confidence interval (CI) will be calculated using the model specified below.

Mathematical model for the calculation of the PI:

By assuming that the number of pregnancies follows a Poisson-distribution, the point estimate and the 95 % CI for the PI can be calculated as follows:

$$PI = x/E,$$

lower 95 % confidence limit of PI = $0.5 \times \chi^2_{(0.025, 2x)} / E$

upper 95 % confidence limit of PI = $0.5 \times \chi^2_{(0.975, 2(x+1))} / E$

where x = number of pregnancies,

E = exposure in 100 woman years (one woman year is 365 days of treatment exposure),

$\chi^2_{(\alpha, df)}$ is the alpha quantile from χ^2 -distribution with df degrees of freedom.

The primary analysis set will be the PAS Year 6 (for the analysis after 6 years), the PAS Year 7 (for the analysis after 7 years) and the PAS Year 8 (for the final analysis after 8 years), respectively. Furthermore, analyses will be repeated for the FAS.

Secondary analysis

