It should be noted that pregnancies that occur within 7 days after the end of exposure will count for the PI calculations.

Furthermore, it should be noted that pregnancies that occur after partial expulsion or first occurrence of non-compliance but before Mirena removal will count for the PI calculations.

Exposure times to be subtracted for Pearl index analyses:

Subjects who apply backup contraception are not at risk or are at lower risk of getting pregnant than subjects who do not apply backup contraception. In case a subject uses backup contraception (e.g., condoms to prevent sexually transmitted disease), the respective 28-day reference period(s) of backup contraception use will be excluded from the exposure time, unless a pregnancy occurred in that 28-day reference period. In the Pearl index analyses, the first 28-day reference period will start at Day 1 Year 6. Missing data will be considered as no use of backup contraception.

Primary analysis:

The primary method for the evaluation of the occurrence of pregnancy is the PI defined as the number of pregnancies per 100 woman-years.

The PIs and the corresponding 2-sided 95% confidence interval (CI) will be calculated using the model specified below.

Mathematical model for the calculation of the PI:

By assuming that the number of pregnancies follows a Poisson-distribution, the point estimate and the 95% CI for the PI can be calculated as follows:

$$PI = x/E,$$

$$\text{lower 95\% confidence limit of PI} = 0.5 \times \chi^2_{(0.025, 2x)} / E$$

$$\text{upper 95\% confidence limit of PI} = 0.5 \times \chi^2_{(0.975, 2(x+1))} / E$$

where x = number of pregnancies,

E = exposure in 100 woman-years,

$\chi^2_{(\alpha, df)}$ is the alpha-quantile from χ^2 -distribution with df degrees of freedom.

All PIs described above will also be presented by parity (no births vs. at least one birth), BMI (<30 kg/m² vs. ≥30 kg/m²) and age at insertion (<18 years vs. 18-25 years vs. 26-35 years, and <18 years vs. 18-35 years), age at baseline (18-25 years vs. 26-35 years vs. >35 years, and 18-35 years vs. >35 years), race and ethnicity. The age at insertion will be calculated as: age at baseline (recorded on the eCRF at baseline, Visit 2) minus 5 years.

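### Conceptions up to 7 days after the end of exposure count for the Pearl Index, but completers' last scheduled test and active contact fall on days 18 to 21, when such a conception may be only 11 days old

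*Protocol*

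**What the plan says.** **Counting rule.** SAP 6.2.1 states that "pregnancies that occur within 7 days after the end of exposure will count for the PI calculations", and Protocol 10.3.2.1 has the same rule. Protocol 9.4.1.2 applies it to reporting: a conception is treated as "suspected to have occurred during study treatment (i.e. up to 7 days after EOT"). Both analysis sections also say that pregnancies after removal count for no PI, so the 7-day sentence has to be read as an exception to that.

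**Last scheduled check.** Protocol 9.2 sets the end-of-study (EOS) contact: "Follow-up contact (EOS) should take place 3 weeks after the EOT (-3 day window allowed"). There is no plus window. Table 9-1, footnote g, adds: "Home pregnancy test is to be done on the day of the 3-week contact".

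**Later contacts.** Protocol 9.2.11 provides a 3-month call, but only for some women: "Subjects who prematurely discontinued study treatment will be contacted by phone", with exceptions for pregnancy, death, and withdrawal of consent with refusal of further contact. The 12-month contact is only for women who stopped because they wished to become pregnant. Completers have neither.

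**Passive reporting.** Protocol 9.4.1.2 tells all women, completers included, to contact the investigator if they become pregnant within 3 months of removal. Sites must report any pregnancy detected in that time. Home test kits are also handed out at the end-of-treatment (EOT) visit.

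**The concern.** The primary variable is a rare event, and the plan extends the period in which it counts to 7 days beyond EOT. The scheduled ascertainment does not clearly reach that far. The contact may be early but not late, so the permitted deviation only shortens the time a late conception has to become detectable. Protocol 7.4.1 recognises that conception around removal is possible: if removal is not timed to menses and "the woman has had intercourse in the week prior to removal, she is at risk of pregnancy".

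Ascertainment also differs by how a woman leaves the study. Most of those who stop early are actively asked at 3 months, while completers must come forward themselves. At stake is the completeness of the numerator of the 3-year PI. An undetected countable pregnancy lowers it, and nothing in the schedule errs in the other direction.

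**Working it through.** **Inputs from the documents.** Counting window: 7 days after the end of exposure (Protocol 10.3.2.1, SAP 6.2.1). Last scheduled test: day 21 after EOT, minus 3 days, so days 18 to 21 (Protocol 9.2, Table 9-1). Target completers: 200. Expected exposure: 832 woman-years (WY). Assumed true PI: 0.2 or 0.3 (all Protocol 10.4). Interval: exact Poisson, with upper limit 0.5 × χ²(0.975, 2(x+1)) / E.

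**The plan's own figures.** With E = 8.32 (hundreds of WY), the upper limit is 0.868 for x = 2 and 1.054 for x = 3, so it stays at or below 1 when x ≤ 2. P(X ≤ 2) is 76.7% at a mean of 0.2 × 8.32 = 1.664 and 54.5% at a mean of 0.3 × 8.32 = 2.496. The protocol states 76% and 55%, so its figures are reproduced.

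**Age of a countable conception at the last test.** Age = test day − conception day. For a conception on day 7 this is 18 − 7 = 11 days at the earliest permitted contact and 21 − 7 = 14 days at the nominal one.

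**Weakly ascertained days per completer.** The documents give no detection lag for a home urine test. Assume it is reliable only from L days after conception, with L between 14 and 21. With the test on day t, the countable days not yet reliably visible number 7 + L − t. Those before removal number max(0, L − t).

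| Lag L | Test day t | Weak days | Before removal | After removal |
|---|---|---|---|---|
| 14 | 21 | 0 | 0 | 0 |
| 14 | 18 | 3 | 0 | 3 |
| 21 | 21 | 7 | 0 | 7 |
| 21 | 18 | 10 | 3 | 7 |

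**In woman-years, 200 completers.** The worst corner is 200 × 10/365 = 5.5 WY. Its part with the device in place is 200 × 3/365 = 1.6 WY, or 0.2% of 832. At the planning PIs this part would carry 1.6 × 0.2/100 = 0.003 to 1.6 × 0.3/100 = 0.005 pregnancies.

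**Conceptions arising in the 7 days after removal.** The time is 200 × 7/365 = 3.84 WY. The rate after removal is not in the documents, so the following are assumptions:

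- Rate unchanged at 0.2 per 100 WY: 0.008.
- 10 per 100 WY, with 5% to 100% of completers unprotected: 0.02 to 0.38.
- 85 per 100 WY, with 5% to 100% unprotected: 0.16 to 3.3.

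The top of the last range supposes that no completer uses any method after removal. All these are conceptions that occur. Only those too early for the test and also never reported would be missed.

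**Effect of one missed pregnancy.** 1/8.32 = 0.12 PI points. For example, counting 2 instead of 3 moves the PI from 0.361 to 0.240 and the upper limit from 1.054 to 0.868.

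**The case against.** The strongest reply is that a negative test on day 18 does not end detection. Every woman is told to report a pregnancy for 3 months after removal, has home kits, and will be investigated if conception may fall within the 7 days. A countable pregnancy is lost only if it is both undetectable at the EOS contact and unreported over the following two months or more. This stands, and it means the days concerned are weakly ascertained, not unobserved. It narrows the gap without closing it, because self-report needs the woman to suspect a pregnancy, and an early negative test may reassure her wrongly.

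The lag is also assumed. At 14 days with a day-21 contact there is no gap at all, and the 10-day figure combines the longest lag with the earliest permitted contact for every woman. That stands too.

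A reader might infer that the gap biases efficacy in Year 8, when the release rate is lowest. The table does not support this: all but at most 3 of the days fall after removal. Exposure also stops at removal (SAP Table 6-1), so the 7-day rule adds pregnancies without matching woman-days. Missing one there mainly reduces an upward allowance.

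Finally, Protocol 7.4.1 and 8.2 describe timing of removal, an overlapping new method or immediate re-insertion, and counselling at Visit 7. These should reduce the number of women unprotected in that week. The Year 6 and Year 7 analyses are barely affected, because continuing users still have the device in place.

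**Conclusion.** The mismatch between counting rule and schedule is real, and it is confined to completers. A countable day-7 conception is 11 to 14 days old at their last scheduled test and last active contact. Under an assumed lag of 14 to 21 days, 0 to 10 countable days per completer are weakly ascertained, with at most 3 before removal. The number of pregnancies missed is probably small but cannot be computed: the documents give neither test sensitivity, nor conception rates after removal, nor the completeness of self-report. The direction is one-sided, since a miss can only lower the count, and each pregnancy is worth 0.12 PI points at 832 WY.

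The move of the upper limit from 1.054 to 0.868 could be read as a failed trial turned into a successful one. The documents do not support that. The visible text uses a limit of 1 only to describe precision in Protocol 10.4 and sets no PI success criterion. This is an inexpensive improvement to ascertainment, not a threat to the primary conclusion.

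**What to change.** In Protocol 9.2 and Table 9-1 (including footnote g), re-time the EOS contact and home test so that a conception on day 7 after EOT is at least 3 weeks old. One option is 4 weeks after EOT with no minus window and a plus window of up to 14 days: 28 − 7 = 21 days, which leaves no weak days even at the 21-day lag. The other sections that refer to a 3-week contact (5, 6.4.1, 9.2.10, 9.2.11 and 9.4.1.1) would need the same edit.

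Alternatively, keep the EOS contact and extend the existing 3-month call to completers. With its −7-day window, that call comes about 90 − 7 − 7 = 76 days or more after a day-7 conception. It would also give completers the same active follow-up as most early discontinuers.

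**Cost.** Re-timing adds no contact. However, the EOS contact defines the last patient's last visit and ends adverse-event collection, so both move about 1 to 3 weeks later (day 28 to 42 against day 21). The alternative adds about 200 short calls. Protocol 11.3 already plans to re-open the database for post-study pregnancy tracking data.

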9.2.1 Optional pre-screening contact

Before the screening visit (Visit 1), an optional pre-screening contact can be arranged and will typically occur via telephone or as a response to an advertisement. During this contact, the study candidate may be interviewed for suitability to participate in the study consistent with the entry criteria of the study. The pre-screening contact may be performed by the investigator, study nurse, or other member of the study staff specifically trained for this task.

After the pre-screening telephone discussion, the subject information form and the informed consent form may be sent to the subject for further information. Regardless of whether the subject information form is sent to the subject, the details of the study must be thoroughly discussed and reviewed with the subject at the screening visit (Visit 1) before obtaining the signed informed consent form.

9.2.2 Screening – Visit 1

At the Screening Visit (Visit 1), the following procedures and assessments will be done:

- Informative discussion about the study; distribution of subject information form.
Note: This must occur at the Screening Visit even if the subject information form was sent to the subject following a pre-screening contact.
- Obtain signed and dated ICF (Section 13.4); allocate the unique SID number (Section 6.5)
- Record the prescribed indication for Mirena and the date of Mirena insertion (documentation required, see also Section 7.1)
- Check of inclusion/exclusion criteria (Sections 6.1 and 6.2)
- Interview for the following:
 - Demographics, alcohol consumption, and smoking habits (Section 9.3.1)
 - Medical history (Section 9.3.2)
 - Reproductive and menstrual history (Section 9.3.3)
 - Concomitant medications (Section 8.1)
 - AEs (Section 9.6.1. The recording period of AEs begins at the signing of the ICF)
- Perform urine pregnancy test (Section 9.6.3.4)
- Assess vital signs and weight (including **height**; Section 9.6.3.1)
- Perform general physical examination (Section 9.6.3.2)
- Perform gynecological examination (with **breast palpation**; Section 9.6.3.3)

- Perform pelvic examination to visualize Mirena removal threads (Section 9.6.3.8)
- Perform safety laboratory tests (including FSH) and urinalysis (Section 9.6.3.7)
- Test for *Chlamydia*; if positive, also test for gonorrhea (Section 9.6.3.6). A single repeat test is permissible if the screening results are positive.
- Obtain cervical smear (Section 9.6.3.5). A cervical smear should be taken at this visit or a documented normal result (using the Bethesda system or a corresponding system) has to have been obtained within 6 months before the Screening Visit (Visit 1). Subjects with ASCUS can be included if they have a HPV DNA test that, according to the standards of the local laboratory, is negative for high-risk HPV. A cervical smear may be repeated once if the screening result is abnormal.

9.2.3 Baseline – Visit 2

This section was changed in Amendment 1, see Section 15.1.1.25.

The following procedures and assessments will be done:

- Re-check inclusion/exclusion criteria (Sections 6.1 and 6.2)
- Age at baseline (Section 9.3.1)
- Perform pelvic examination to visualize Mirena removal threads (Section 9.6.3.8)
- Perform urine pregnancy test (Section 9.6.3.4)
- Blood sample for PK (**all subjects**) (Section 9.5.1)
- Subject satisfaction with Mirena (Section 9.7.4)
- Interview for the following:
 - Concomitant medications (Section 8.1)
 - AEs (Section 9.6.1)
- Dispense and explain the subject's daily eDiary device (Section 9.7.1), remind the subject to start the eDiary at the day of the visit (i.e. recording of uterine bleeding and back-up contraception)
- Dispense home pregnancy kits with instructions (Section 9.6.3.4)
- Dispense alkaline hematin kit with instructions for subjects in HMB group

9.2.4 6-month visit – Visit 3

The following procedures and assessments will be done:

- Perform pelvic examination to visualize Mirena removal threads (Section 9.6.3.8)
- Perform urine pregnancy test (Section 9.6.3.4)
- Blood sample for PK (Note: **subjects randomized to this visit**) (Section 9.5.1)
- Interview for the following:
 - Concomitant medications (Section 8.1)
 - AEs (Section 9.6.1)
 - Continuing need for contraception (Section 9.7.1)

- Dispense home pregnancy kits with instructions (Section 9.6.3.4)
- Review completed (monthly) eDiary, including information on uterine bleeding and back-up contraception.
- Dispense alkaline hematin kit with instructions for subjects in HMB group

9.2.5 12-month visit – Visit 4 (End of Year 6 of Mirena use)

This section was changed in Amendment 1, see Section 15.1.1.1.

The following procedures and assessments will be done:

- Assess vital signs and weight (Section 9.6.3.1)
- Perform general physical examination (Section 9.6.3.2)
- Perform gynecological examination (with **breast palpation**; Section 9.6.3.3)
- Perform pelvic examination to visualize Mirena removal threads (Section 9.6.3.8)
- Perform urine pregnancy test (Section 9.6.3.4)
- Perform safety laboratory test and urinalysis (Section 9.6.3.7)
- Blood sample for PK (Note: **subjects randomized to this visit**) (Section 9.5.1)
- Interview for the following:
 - Concomitant medications (Section 8.1)
 - AEs (Section 9.6.1)
 - Continuing need for contraception (Section 9.7.1)
- Dispense home pregnancy kits with instructions (Section 9.6.3.4)
- Review completed (monthly) eDiary, including information on uterine bleeding and back-up contraception.
- Subject satisfaction with Mirena (Section 9.7.4).

9.2.6 18-month visit – Visit 5

The following procedures and assessments will be done:

- Perform pelvic examination to visualize Mirena removal threads (Section 9.6.3.8)
- Perform urine pregnancy test (Section 9.6.3.4)
- Blood sample for PK (Note: **subjects randomized to this visit**) (Section 9.5.1)
- Interview for the following:
 - Concomitant medications (Section 8.1)
 - AEs (Section 9.6.1)
 - Continuing need for contraception (Section 9.7.1)
- Dispense home pregnancy kits with instructions (Section 9.6.3.4)
- Review completed (monthly) eDiary, including information on uterine bleeding and back-up contraception.
- Dispense alkaline hematin kit with instructions for subjects in HMB group

9.2.7 24 –month visit – Visit 6 (End of Year 7 of Mirena use)

The following procedures and assessments will be done:

- Assess vital signs and weight (Section 9.6.3.1)
- Perform general physical examination (Section 9.6.3.2)
- Perform gynecological examination (with **breast palpation**; Section 9.6.3.3)
- Perform pelvic examination to visualize Mirena removal threads (Section 9.6.3.8)
- Perform urine pregnancy test (Section 9.6.3.4)
- Perform safety laboratory test and urinalysis (Section 9.6.3.7)
- Blood sample for PK (Note: **subjects randomized to this visit**) (Section 9.5.1)
- Interview for the following:
 - Concomitant medications (Section 8.1)
 - AEs (Section 9.6.1)
 - Continuing need for contraception (Section 9.7.1)
- Dispense home pregnancy kits with instructions (Section 9.6.3.4)
- Review completed (monthly) eDiary, including information on uterine bleeding and back-up contraception
- Subject satisfaction with Mirena (Section 9.7.4).

9.2.8 30-month visit – Visit 7

This section was changed in Amendment 1, see Section 15.1.1.21.

The following procedures and assessments will be done:

- Perform pelvic examination to visualize Mirena removal threads (Section 9.6.3.8)
- Perform urine pregnancy test (Section 9.6.3.4)
- Interview for the following:
 - Concomitant medications (Section 8.1)
 - AEs (Section 9.6.1)
 - Continuing need for contraception (Section 9.7.1)
- Dispense home pregnancy kits with instructions (Section 9.6.3.4)
- Review completed (monthly) eDiary, including information on uterine bleeding and back-up contraception.
- Dispense alkaline hematin kit with instructions for subjects in HMB group.

Discuss the contraceptive options available after the study treatment with the subject (see Section 8.2).

9.2.9 36-month visit, EOT – Visit 8 (End of Year 8 of Mirena use)

This section was changed in Amendment 1, see Section 15.1.1.17.

The following procedures and assessments will be done:

- Assess vital signs and weight (Section 9.6.3.1)
- Perform general physical examination (Section 9.6.3.2)
- Perform gynecological examination (with **breast palpation**; Section 9.6.3.3)
- Perform pelvic examination to visualize Mirena removal threads (Section 9.6.3.8)
- Obtain cervical smear (Section 9.6.3.5)
- Perform urine pregnancy test (Section 9.6.3.4)
- Perform safety laboratory test and urinalysis (Section 9.6.3.7)
- Blood sample for PK (**all subjects**) (Section 9.5.1)
- Interview for the following:
 - Concomitant medications (Section 8.1)
 - AEs (Section 9.6.1)
 - Continuing need for contraception (Section 9.7.1)
- Dispense home pregnancy kits with instructions (Section 9.6.3.4)
- Review completed (monthly) eDiary, including information on uterine bleeding and back-up contraception.
- Collect eDiary device (Section 9.7.1)
- Subject satisfaction with Mirena (Section 9.7.4)
- Remove the Mirena (Section 9.7.3)
- Complete Mirena removal ease (investigator) and pain (subject) assessment

9.2.10 3-week follow-up call (EOS)

All subjects will be contacted 3 weeks after EOT (i.e. after Mirena removal) to collect information on any pregnancy detected shortly after the end of study treatment, see Section 9.4.1.

9.2.11 3-month follow-up contact for post-study pregnancies

This section was changed in Amendment 1, see Section 15.1.1.6.

Subjects who prematurely discontinued study treatment will be contacted by phone unless the reason for discontinuation is “pregnancy”, “death”, or “withdrawal by subject” where the subject has withdrawn main consent during study conduct and wishes to stop future contact with the site. For subjects that had withdrawn consent during study, but consented to post study participation follow-up, post treatment pregnancy tracking information is expected. At this time, subjects will be asked if they have been pregnant after the study (i.e. after the 3-week follow-up call). This contact is part of the Post-Treatment Pregnancy Tracking (PTPT) process, see Section 9.4.1.

9.2.12 12-month follow-up contact for return-to-fertility

This section was changed in Amendment 1, see Section 15.1.1.6.

Subjects that prematurely discontinued treatment due to ‘Wish for pregnancy’ will be contacted and asked about pregnancies that occurred within 12 months after end of treatment (EOT, i.e. removal of Mirena). If a subject was not pregnant at 3 month contact and no longer wished to become pregnant, a 12-month contact is not required. If subject was “Lost to Follow-up” at 3 months, a 12-month contact is required. This contact is part of the Post-Treatment Pregnancy Tracking (PTPT) process, see Section 9.4.1.

